2.9 STATISTICAL ANALYSIS

The overarching goals for the pilot trial are to evaluate safety, efficacy and feasibility of a LTLR-WB prehospital through in-hospital protocol to plan for the successful execution of a large, multicenter clinical trial. All analyses will be performed based on the intent-to-treat principle for the prehospital randomization and analyses will include all enrolled patients grouped by randomization assignment. This pilot study will guide the calculation needed for the large, multicenter clinical trial and will provide estimation for intra-cluster correlation coefficient and sample size variation across clusters. We will report 95% confidence intervals for all measurements

Safety and Efficacy Analysis: 28-day mortality is the primary safety and efficacy outcome and will be compared across randomized groups. Utilizing intention to treat principles we will compare the LTLR-WB and Standard of Care arms using a pooled Z test for comparing two independent proportions. We will additionally perform survival analysis for all mortality outcomes including 3hr, 6hr, 24hr, and 28day time points across the two arms of the study testing the differences using log rank test.

Eligibility, Enrollment, and Subject Accrual Anlaysis: The feasibility of enrollment will be evaluated by determining 1) the number of patients that meet the eligibility criteria for the trial; 2) the proportion of eligible patients that can be randomized and 3) the proportion of eligible patients who are enrolled in the trial. These proportions will be estimated directly as the observed ratio of numbers of patients, and 95% confidence intervals will be calculated to understand the likely range of values for a larger study with a comparable research protocol. The reasons why patients are not enrolled including frequencies of individual exclusions and the proportion of patients declining participation or not able to be randomized will be described. Rate of subjects' accrual per month with 95% C.I. will be calculated.

Adherence and Minimization of Bias: Adherence rates for each treatment arm of the protocol will be ascertained as the proportion of enrolled patients who adhere to the intervention (LTLR-WB vs. standard care) as assigned. Estimated proportions and 95% confidence intervals will be created. The trial has been designed to negate intervention arm crossover and maximize follow-up completion.

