Statistical Distributions of Enrolled Sample of Patients: Descriptive statistics, including means, standard deviations, medians, interquartile ranges, minimums, maximums, and frequency distributions, will be examined for all relevant measures. Transformations of measures will be considered based on distribution diagnostics and outlier analyses. The baseline characteristics of the patients in the entire trial will be described and 95% confidence intervals will be calculated to identify potential differences in baseline characteristics.

- 1. Estimated proportions and means and 95% confidence intervals will be created for each outcome using the data from the entire pilot trial (i.e. combining the data from the two assigned treatment arms).
- 2. Absolute and relative differences for continuous levels and event rates by assigned treatment will be estimated and 95% confidence intervals will be calculated to identify potential treatment differences for safety and for study planning purposes. Subgroup analyses will be exploratory and be based on baseline factors specified prior to the initiation of the trial.
- **3.** Descriptive statistics, including means, standard deviations, medians, interquartile ranges, minimums, maximums, and frequency distributions, will be examined for all relevant measures.

- Transformations of measures will be considered based on distribution diagnostics and outlier analyses.
- The baseline characteristics of the patients in the entire trial will be described and 95% confidence intervals will be calculated to identify potential differences in baseline characteristics.

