Sample Size Justification for Pilot Trial: Assuming a baseline in-hospital mortality risk of 33% in the control arm as was demonstrated in the recently completed PAMPer trial with all cause in-hospital mortality as the primary outcome, enrolling **56 patients in each arm, 112 total patients** and using a 2 sided alpha of 0.05, the study will have a 80% power to detect a 22% (33% to 11%) or greater difference in in-hospital mortality. Based upon current PAMPer clinical outcome data and the additional benefit attributable to LTLR-WB when it is initiated in the prehospital setting, the current proposed mortality difference is clinically meaningful and of sufficient magnitude to influence clinical practice for a pilot trial. The above sample size will provide more than sufficient power for the originally planned feasibility outcomes as we have increased our sample size by 24%. The above power analysis was generated assuming 2 sequential tests using the O'Brien-Fleming spending function to determine test boundaries which are depicted in the following table and graph.

Details	Details when Spending = O'Brien-Fleming, N1 = 56, N2 =56, P1 = 0.1100, P2 = 0.3300							
		Lower	Upper	Nominal	Inc	Total	Inc	Total
Look	Time	Bndry	Bndry	Alpha	Alpha	Alpha	Power	Power
1	0.50	-2.96259	2.96259	0.003051	0.003051	0.003051	0.164669	0.164669
2	1.00	-1.96857	1.96857	0.049002	0.046949	0.050000	0.636252	0.800921
Drift 2.	81024							

Based upon the busy air medical service at the University of Pittsburgh, the bases to be utilized for the pilot trial, 61 patients who met all inclusion and exclusion criteria for the current proposed pilot trial, were admitted to Presbyterian Hospital, consented and were enrolled (www.pamperstudy.com) over a 12 month period 6/2015-5/2016. Based upon a planned enrollment period of 2.5 years, this sample size is feasible after accounting for consent rates and exclusions.

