If the PI and study team plan to modify the study, they will submit the amendment to the University of Pittsburgh HRPO along with all study documents to be changed (i.e. protocol, consent form, etc.) Once IRB approval is obtained, the study team will submit the changes to the NIH at the next reporting cycle unless earlier notification is warranted. If it is a significant change, the PI will request approval by the NIH Program Officer and DSMB prior to modification. Any changes will also be reviewed by the Office for Investigator-Sponsored IND and IDE Support (O3IS) for determination if the change requires prospective FDA review or if it can be submitted at annual report.

Data Analysis Plan Overall guideline:

- 1. Nature of this study: Pilot study
- 2. Overall objectives: Evaluate safety, efficacy, and feasibility of a LTLR-WB prehospital thru in-hospital protocol. The study will provide estimation for intra-cluster correlation coefficient and sample size variation across clusters for the design for a future full scope large clinical trail
- 3. Analysis Principle: Intent-to-treat for the prehospital randomization assignment. 95% confidence intervals for all measurements

Safety and Efficacy Analysis:

- 1. In-hospital mortality is the primary safety and efficacy outcome and will be compared across randomized groups.
- 2. LTLR-WB and Standard of Care arms will be compared using a pooled Z test of two independent proportions.
- 3. Survival analysis will be conducting looking at median survival at 3hr, 6hr, 24hr, and 28day time points across the two arms of the study testing the differences using log rank test.

Eligibility, Enrollment, and Subject Accrual:

The feasibility of enrollment will be evaluated by determining, ratio of the following parameters will be calculated along with 95% confidence intervals:

- 1) the number of patients that meet the eligibility criteria for the trial;
- 2) the proportion of eligible patients that can be randomized and

3) the proportion of eligible patients who are enrolled in the trial.

Additionally:

1. The reasons of not enrollment will be recorded with related frequency and percentages.

- 2. Frequency of patients eligible but not enrolled will be recorded
- 3. Frequency of patients randomized but not included in the study will be recorded
- 4. Rate of subjects' accrual per month with 95% C.I. will be calculated.

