6.5.1 Protection Against Risks

General Risks of Study Protocol and Procedures

Data collected will include a review of the air medical patient care report(s), Emergency Department and electronic/ paper hospital records. Prehospital Data: Demographics, air medical response times (call receipt to arrival, arrival at patient side,) injury characteristics, vital signs, prehospital resuscitation volumes, prehospital interventions (needle decompression, chest tubes)

referring hospital vitals, and interventions will be recorded. In-Hospital Data: Demographics, shock severity (base deficit, lactate), injury characteristics, ED vitals, ED interventions (chest tubes, intubation), injury severity, operative interventions and timing of interventions, injury severity score, ICU days, ventilator days, length of stay, multiple organ dysfunction scores (daily), nosocomial infectious outcomes, blood gas results, chest x-ray reads, transfusion of blood and blood components, resuscitation requirements, all primary and secondary outcomes will be recorded.

Data Entry and Storage: MACRO and associated internet technology affiliates at the University of Pittsburgh will create web-based data entry platform to collect necessary information for the proposed pilot study.

All research interventions/activities will be conducted in private patient care areas. The collection of sensitive information about subjects is limited to the amount necessary to achieve the aims of the research, so that no unneeded sensitive information is being collected.

A Case Report Form will be completed for each subject enrolled into the clinical study. The Investigator will attest that all clinical and laboratory data entered on the CRF are complete, accurate and authentic using a signoff page within the data entry platform. A key linking the subject to the code number will be kept locked in a secure location and will be available only to the investigators. The data and samples will be retained indefinitely and used for future testing. Data from this study, without the subject's identity, may be reported in scientific meetings, articles or other appropriate communications.

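### The primary mortality test is unadjusted, so collected pre-treatment predictors of death (age, qualifying blood pressure and heart rate) add no precision to the final analysis

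*Combined protocol and SAP*

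**What the plan says.** Section 2.9 (Safety and Efficacy Analysis) states that "28-day mortality is the primary safety and efficacy outcome and will be compared across randomized groups", and that "we will compare the LTLR-WB and Standard of Care arms using a pooled Z test for comparing two independent proportions". The data analysis plan in section 6.4.2 repeats the method: "LTLR-WB and Standard of Care arms will be compared using a pooled Z test of two independent proportions". The interim analysis in 6.4.2 and Table 2 of Appendix 8 name the same test. The supporting survival analysis is an unadjusted log-rank test. Section 2.9 names 28-day mortality, while 6.4.2 and Table 2 name in-hospital mortality. That discrepancy is a separate matter, and this point applies to either endpoint.

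The only stated use of baseline data to compare the arms is descriptive: "95% confidence intervals will be calculated to identify potential differences in baseline characteristics". The values themselves are available:

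- Section 6.5.1 lists demographics among the prehospital data, together with "injury characteristics, vital signs, prehospital resuscitation volumes, prehospital interventions".
- Qualifying systolic pressure and heart rate decide entry (section 3.2). Section 3.3 makes them source-documented, by verbal report where necessary.
- Age is a row of Table 1 in Appendix 8. GCS is also a row, without a time of measurement.

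Randomisation (section 2.6) assigns whole helicopter bases by month. No patient-level stratification is described.

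**The concern.** Age and initial haemodynamic state are plausible strong predictors of death after trauma, and both are fixed before study treatment. An unadjusted comparison leaves the outcome variation they explain in the standard error. It also leaves any chance difference in initial severity in the estimate. Mortality is the only outcome with a power calculation, and section 2.9 describes the targeted difference as large enough to influence practice, so precision matters even in a pilot. If adjustment is not prespecified, any adjusted result will have been chosen after an open-label trial, when it carries least weight.

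**Working it through.** **1. Inputs from the documents.** Section 2.9: 56 per arm; 33% versus 11%; "using a 2 sided alpha of 0.05"; two looks, at information times 0.50 and 1.00, with boundaries 2.96259 and 1.96857. The control rate is introduced with "Assuming a baseline in-hospital mortality risk of 33% in the control arm".

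**2. The plan's own figure.** The pooled rate is (0.33 + 0.11)/2 = 0.22. Drift = 0.22 / sqrt(0.22 × 0.78 × 2/56) = 0.22 / 0.07829 = 2.810. With correlation sqrt(0.5) between looks and the stated boundaries, first-look power is 0.1647, total power 0.8010 and total alpha 0.0500. The plan states 0.164669, 0.800921 and 0.050000, so its power reproduces for the unadjusted test.

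**3. Approximate gain.** If pre-treatment covariates explain a share R² of outcome variance, the drift becomes 2.810 / sqrt(1 − R²), and the equivalent sample size is 112 / (1 − R²). R² is an assumption.

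| Assumed R² | Equivalent N | Two-look power |
|---|---|---|
| 0 | 112 | 80.1% |
| 0.10 | 124 | 84.1% |
| 0.20 | 140 | 88.0% |
| 0.30 | 160 | 91.8% |

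**4. Simulation at the final boundary.** The setting was 56 per arm, independent patients and three covariates, with 4,000 trials per setting. The adjusted estimate is the mean over all patients of p̂(treated, X) − p̂(control, X) from a logistic model. Its influence-function standard error had a degrees-of-freedom correction. AUC is an assumption.

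| Assumed AUC | Raw Z power | Adjusted power | Change (points) |
|---|---|---|---|
| No prediction | 83.8% | 82.7% | −1.1 |
| 0.70 | 81.6% | 84.1% | +2.5 |
| 0.77 | 84.3% | 89.2% | +4.9 |
| 0.84 | 83.3% | 92.2% | +8.9 |

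The raw figures exceed 80.1% because the plan's drift uses the pooled variance. The unpooled drift of 2.915 gives 82.9%. The change within each row is therefore the relevant comparison. Type I error in these runs was 4.9–5.6% adjusted and 5.0–5.9% raw. Without the correction, the adjusted figure was 5.9–6.4%.

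**5. Adjusting at both looks.** Expected deaths under the design rates are 0.22 × 56 = 12.3 at the interim look and 0.22 × 112 = 24.6 at the end. Two-look simulation with three covariates gave:

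| Statistic | Look-1 type I error | Total type I error |
|---|---|---|
| Planned | 0.305% | 5.0% |
| Raw Z | not tabulated | 5.2–5.8% |
| Adjusted, uncorrected SE | 0.7–0.8% | 6.2–7.2% |
| Adjusted, degrees-of-freedom correction | 0.5–0.6% | 5.5–6.7% |

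The correction repairs this only in part. A real gain remained at the final analysis: about 83% raw to 87–90% adjusted with correction.

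**6. Raw test at look 1, adjusted test at the end.** If each test holds its nominal level, total alpha cannot exceed 0.003051 + 0.049002 = 0.052053, whatever the correlation between the two statistics. Mixing them costs at most about 0.2 points. The larger risk is the small-sample behaviour of the adjusted test itself.

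**7. Chance imbalance.** With 56 independent patients per arm, a standardised covariate difference has standard error sqrt(2/56) = 0.189. The chance that it exceeds 0.25 in either direction (0.25/0.189 = 1.32) is 19%. For at least one of two independent covariates it is 1 − 0.814² = 34%.

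**The case against.** The strongest reply is that nothing is broken. Under independence, a pooled Z test of randomised arms is valid. Chance imbalance is already counted in its alpha, the stated power is correct, and the trial is a pilot. All of that stands, so the point concerns efficiency and the absence of a prespecified adjusted analysis.

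Several stronger readings are tempting, but the documents do not support them:

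- **That the unadjusted result is biased.** Omitting covariates does not bias a randomised comparison. The imbalance figures above describe how far one realised trial may drift.
- **That imbalance is aggravated by few base-months.** Monthly assignment over 2.5 years gives 30 base-months from a single base and 90 from three. Section 2.1 plans several bases without fixing the number, and blocks spread the arms over time.
- **That baseline data are never used.** Section 2.8 predefines subgroup analyses of the primary outcomes, for example scene versus referral and preinjury anticoagulation. They are not adjustment, but they do use baseline data.
- **That pre-treatment GCS is on hand.** Table 1 gives no timing and also holds later items such as ED disposition and procedures. The prehospital list in 6.5.1 does not name GCS.
- **That the adjusted statistic can simply replace the Z test at both looks.** Step 5 shows that it overspends alpha at the first.

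Two further limits also stand. Qualifying pressure and heart rate are range-restricted by the entry criteria and may come from verbal report, which could weaken their prediction. The simulations assume independent patients and so say nothing about base-month clustering, which is a separate problem with the same test.

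**Conclusion.** The point holds as one of lost precision. The primary mortality test is valid apart from clustering and is powered as stated, but it uses none of the pre-treatment information that the trial collects. At 112 patients, adjustment would add about 2.5 to 9 points of power if the covariates reach an AUC of 0.70 to 0.84, and would cost about 1 point if they do not predict. These figures assume independent patients, the design rates of 33% and 11%, and a prognostic strength that the documents do not supply. Where the adjusted test's type I error runs slightly above 5%, part of the apparent gain comes from that excess. The improvement is worth making, but it does not correct an invalid result, and the gain is supported only for the final analysis.

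**What to change.** Amend sections 2.9 and 6.4.2 and Table 2 of Appendix 8 as follows:

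1. **Final analysis.** Prespecify a marginal risk difference with 95% CI, standardised from a logistic model containing arm, age and qualifying shock index (heart rate divided by systolic pressure at qualification). Do not use the arrival shock index, which section 2.8 lists as an outcome. Add GCS only if a value taken before study treatment is available. With about 25 deaths expected, the covariate set should stay this small and fixed.
2. **Standard error.** Use a small-sample correction that also respects the base-month clusters. Before locking the plan, check by simulation, with clustering included, that total type I error stays near 5%.
3. **Interim look.** Keep the raw pooled Z test and its O'Brien-Fleming boundary.
4. **Missing covariates and fallback.** State a simple rule that does not depend on arm or outcome, such as imputing the overall mean. Cover patients enrolled after ED arrival (section 5.1). Use the raw difference if the model does not converge, and report it as the supporting analysis in any case.
5. **Table 1.** Add rows for qualifying systolic pressure and heart rate, and state when GCS was measured.

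The cost is SAP wording, one model to prespecify, a modest simulation, and confirmation that the case report form captures the qualifying values. Including GCS may also require a data field with a defined time.

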2.6 RANDOMIZATION

Procedures Assuring Adherence to Randomized Assignment: Enrollment will occur in the prehospital phase of the trial and LTLR-WB or prehospital standard of care will be provided based upon randomization assignment. Prehospital providers will designate the patient as enrolled and notify receiving staff of the treatment arm. Research staff will be present upon arrival and will communicate directly with blood banking staff/anesthesia and the trauma team regarding the randomization arm of the patient. Once in-hospital, LTLR-WB randomized patients may receive LTLR-WB transfusion as indicated during this acute resuscitation phase of in-hospital care up to 6 units in-hospital and 8 units of LTLR-WB total.

Randomization and Blinding: A single stage cluster randomization scheme will be utilized. Designated air medical bases at the University of Pittsburgh will be block randomized and assigned to the LTLR-WB arm or Standard of Care (control) arm for 1 month time intervals. The cluster design will be at the level of the helicopter base. The block scheme will vary randomly between 2 and 4 month block sizes over the period of enrollment for the trial. Randomization assignments will be determined prior to the start of the bases enrollment following the above single stage cluster design using standard computerized randomization software. Communication with the blood bank transportation services and each respective air base will occur and an annual schedule of randomization assignment will be distributed to each study air base. This specific randomization scheme is required due to the limited supply of O+ LTLR-WB and also due to the logistics and delivery of the intervention in the prehospital setting. The

proposed pilot trial will be an open label trial as blood product transfusion requires appropriate documentation and essential look back procedures.

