5. RECRUITMENT AND INFORMED CONSENT PROCEDURES

5.1 RECRUITMENT METHODS:

Subjects will be enrolled under "Exception from Informed Consent for emergency situations."

Subjects will be identified by prehospital air medical personnel at the scene, in transit or when being picked up from a referring facility. Subjects not enrolled by prehospital personnel but who meet all inclusion and no exclusion criteria may be identified and enrolled by research personnel after arrival to the ED and will be analyzed based on the arm assignment from which they originated per the intention to treat analytic plan.

In cases where the subject is incapacitated and unable to provide direct consent and an appropriate LAR is not present in the hospital, the consent will be obtained by phone/fax or electronically. The study will be discussed with the LAR over the telephone. If the LAR agrees, the consent form (ICF) will be sent electronically (email, fax, DocuSign, etc.) to the LAR. The investigator will go over the ICF with the Legally Authorized Representative. If the LAR agrees to participate in the research, the LAR will sign the ICF and send back to the Principal investigator electronically. An electronic picture of the signed signature page.forwarded to the consenting Investigator, will be accepted. The consent form may also be sent to the LAR via DocuSign, where the document can be reviewed in detail and digitally signed.

We will also send a postage paid envelope to the LAR for returning of the original complete signed informed consent whenever consent is obtained via email or fax.

If initial consent is obtained via LAR, the study team will routinely monitor the subject for capacity to consent while still admitted to the hospital. If it is determined by the Investigator, in conjunction with the assessment of the clinical team, that the subject has regained capacity, the Investigator will conduct the inform consent discussion and attempt to obtain continuing consent.

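### Helicopter bases are randomised month by month, but the primary and interim tests, the log-rank test and the 80% power calculation treat patients as independent; the effect is modest.

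*Combined protocol and SAP*

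**What the plan says.** **Allocation.** Section 2.6 states: "The cluster design will be at the level of the helicopter base". Bases are "assigned to the LTLR-WB arm or Standard of Care (control) arm for 1 month time intervals", and "The block scheme will vary randomly between 2 and 4 month block sizes over the period of enrollment for the trial". Section 5.1 is consistent with this: a patient found eligible only after arrival "will be analyzed based on the arm assignment from which they originated per the intention to treat analytic plan". No patient is randomised individually.

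**Analysis.** Section 2.9 compares the arms on the primary mortality outcome "using a pooled Z test for comparing two independent proportions". Section 6.4.2 repeats this test for the final analysis and for the interim look that carries the stopping rule, and Table 2 in Appendix 8 lists it again. Survival is compared by "testing the differences using log rank test". No base or month term appears in any between-arm analysis.

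**Power.** Sections 2.9 and 6.4.7 give 56 patients per arm, 33% against 11% mortality, two-sided alpha 0.05, two looks with O'Brien-Fleming spending, and 80% power (printed drift 2.81024, total power 0.800921). They state no intra-cluster correlation (ICC) or design effect.

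**Clustering elsewhere.** Section 2.9 says that the pilot "will provide estimation for intra-cluster correlation coefficient and sample size variation across clusters", and section 6.4.2 ties this to "sample size variation across clusters for the design for a future full scope large clinical trail". The correlation is thus a quantity to be estimated for the next trial and is not used in this one.

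**The concern.** A test that assumes independent patients is valid when patients are allocated independently, or when patients who share an allocation are no more alike than patients who do not. Here all patients from one base in one month share an arm. If they also share something that affects mortality in that month, the variance of the arm difference is larger than the pooled Z test assumes.

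Three things are at stake. The primary test and the interim stopping test may reject a true null hypothesis more than 5% of the time. The confidence intervals for the arm difference, which are meant to inform the large trial, may be too narrow. And the 80% was worked out with no allowance for this, so a test that does hold 5% may have less.

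**Working it through.** **1. Reproduce the plan's power.** Inputs from section 2.9: mortality 0.33 and 0.11 (mean 0.22), 56 per arm, looks at half and full information, boundaries 2.96259 and 1.96857.

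- Drift = 0.22 / sqrt(2 × 0.22 × 0.78 / 56) = 2.81024, the printed value.
- Two-look bivariate normal (correlation sqrt(0.5)): power 0.8010 (printed 0.800921), alpha 0.0500.

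The match requires a design effect of exactly 1. The boundaries themselves are correct.

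**2. Is the 24% sample size increase a hidden allowance?** No. Section 2.9 links it to the feasibility outcomes. Also, 80% power under independence already needs 55.9 per arm, so 56 leaves nothing over.

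**3. Which correlation matters?** Each base alternates between arms, so a stable base effect falls on both. In a simulation of the final-look test with 2 to 4 bases, a base-level ICC of 0.05 and no month effect, type I error stayed at 5.0% to 5.2%. The relevant quantity is the excess ICC: the correlation between two patients from one base in the same month, minus that for the same base in different months.

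**4. Size by formula.** Assumptions: B equal bases, M months, 112 patients spread at random.

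- Size-weighted patients per base-month: m = 1 + 111/(M × B).
- Design effect: DE = 1 + (m − 1) × excess ICC.
- Planned test: the Z statistic has variance DE and drift 2.81024.
- Test corrected to hold 5%: variance 1 and drift 2.81024/sqrt(DE).

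The 14 bases are the total in section 2.1; 3 is an assumed low value. The 30 months are the enrolment period in section 2.9. Worked case, B = 3, M = 30, ICC 0.10: m = 1 + 111/90 = 2.233; DE = 1 + 1.233 × 0.10 = 1.123.

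| Bases | Months | Excess ICC | DE | Planned test: type I error | Planned test: power | Corrected test: power |
|---|---|---|---|---|---|---|
| 3 | 30 | 0.02 | 1.025 | 5.3% | 79.8% | 79.1% |
| 3 | 30 | 0.05 | 1.062 | 5.7% | 79.4% | 77.7% |
| 3 | 30 | 0.10 | 1.123 | 6.5% | 78.8% | 75.4% |
| 5 | 30 | 0.05 | 1.037 | 5.4% | 79.7% | 78.7% |
| 5 | 30 | 0.10 | 1.074 | 5.9% | 79.3% | 77.2% |
| 14 | 30 | 0.02 | 1.005 | 5.1% | 80.0% | 79.9% |
| 14 | 30 | 0.05 | 1.013 | 5.2% | 79.9% | 79.6% |
| 14 | 30 | 0.10 | 1.026 | 5.3% | 79.8% | 79.1% |
| 3 | 22 | 0.10 | 1.168 | 7.1% | 78.4% | 73.7% |

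The 22-month row uses the accrual in section 2.9, 61 patients in 12 months: 112/(61/12) = 22.0 months.

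**5. Check by simulation.** Settings: 12,000 trials per cell, looks at 56 and 112 patients, random 2- and 4-month blocks within base, beta-binomial base-months, 1,999 re-draws for the randomisation test. Monte Carlo error (95%) is about ±0.4 points for type I error and ±0.8 for power.

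| Bases | Months | Excess ICC | Planned Z: type I error, power | Randomisation test: type I error, power |
|---|---|---|---|---|
| 3 | 30 | 0.05 | 5.9%, 81.1% | 5.1%, 77.8% |
| 3 | 30 | 0.10 | 6.5%, 80.9% | 4.8%, 76.0% |
| 5 | 30 | 0.05 | 5.5%, 81.9% | 4.7%, 79.4% |
| 5 | 30 | 0.10 | 5.9%, 81.7% | 4.9%, 78.3% |
| 14 | 30 | 0.05 | 5.2%, 81.9% | 4.9%, 80.7% |
| 14 | 30 | 0.10 | 5.5%, 81.4% | 5.0%, 80.0% |
| 3 | 22 | 0.10 | 6.9%, 80.3% | 4.6%, 73.2% |

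With no excess correlation the planned test has type I error of 5.0% to 5.1% and power of about 82%; the randomisation test has 4.7% to 4.8% and 80.2% to 81.1%. Simulated power for the planned test lies slightly above the formula because the formula uses the pooled variance under the alternative.

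**The case against.** The best defence is that the harm depends on an excess same-month correlation for which the documents give no value and no mechanism. Base-months are also tiny. With 30 months, the share of patients alone in their base-month is about (1 − 1/(30 × B))^111, which is 77% for 14 bases and 29% for 3. At an excess ICC of 0.02, type I error is 5.1% to 5.3%. This is a pilot that sets out to estimate the ICC, so clustering was not overlooked. All of this stands, and it limits the size of the point. It does not supply an analysis that follows the randomisation, and no other section does.

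A randomisation test also has a condition of its own: re-drawing the schedule over a fixed set of patients assumes that enrolment does not depend on arm. The trial is open label, bases hold an annual schedule, and patients can be enrolled after arrival. That caution stands too. A model-based analysis that respects the base-month is an acceptable alternative.

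A reader might infer more than the documents support:

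- **A parallel-cluster design effect.** With 6 bases and ICC 0.05, whole-base clusters would give DE 1.88 and power of 53%. That ignores the monthly switching of arms and overstates the problem.
- **That the 80% is wrong for the planned test.** Simulated power of that test is at least 80.3% in every cell above.
- **That 5% and 80% can hold together only with zero excess correlation.** With 14 bases and ICC 0.10, the simulated randomisation test has 5.0% and 80.0%.
- **That the type I inflation and the power loss add up.** They belong to two different tests.

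**Conclusion.** The mismatch between design and analysis is established from the text, and the power calculation demonstrably contains no allowance for clustering. Its consequence is modest and conditional. If the excess same-month correlation within a base is above zero, the planned Z test exceeds its nominal 5% and its confidence intervals are too narrow, with power still near 80%. Under the assumed 3 to 14 equal bases, 30 months and excess ICC of 0.05 to 0.10, type I error is about 5.2% to 6.5%; the 22-month, 3-base, 0.10 case reaches about 7%. A test that holds 5% gives up at most about 5 points over 30 months by the plan's own formula (80.1% − 75.4% = 4.7). Confidence in the mismatch is high. Confidence in the size is low, because the ICC and the number of bases are assumptions. The point should be fixed because this is the primary test and the one that governs stopping; it is not a fatal flaw.

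**What to change.** In sections 2.9 and 6.4.2 (final and interim) and in Table 2, replace the independence-based Z test with one pre-specified analysis that respects the base-month allocation. Two suitable choices:

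- a randomisation test of the mortality difference that re-draws the schedule within each base using the same random 2- and 4-month blocks, judged at the existing nominal levels 0.003051 and 0.049002, with enough re-draws to resolve the smaller one (for example 9,999);
- a cluster-robust or GEE analysis with the base-month as cluster and a small-sample correction.

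Treat the log-rank test and the confidence interval for the arm difference in the same way.

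In sections 2.9 and 6.4.7, state that the 80% was calculated for independent patients, with no allowance for correlation within a base-month. If a power range is added, compute it by simulation for the test actually chosen, over stated assumptions on excess ICC, number of bases and duration (22 to 30 months), and label it illustrative. The formula figures above should not stand in for it, since they do not describe any particular replacement test.

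The cost is SAP wording and a little programming. If there is no clustering, the randomisation test loses about 1 to 2 points of power (80.2% to 81.1%, against about 82%). Enrolment does not change.
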